4.2. Secondary Endpoints

- 1) Pancreatic lesions detection rate: It was calculated by dividing the total number of patients being detected pancreatic lesions by the number of EUS.
- 2) Cholangiopancreatic duct lesions detection rate: It was calculated by dividing the total number of patients being detected cholangiopancreatic duct lesions by the number of EUS.
- 3) The average number of scanning in the pancreatic standard station of endoscopic ultrasonography: It was calculated by dividing the total number of scanning in the pancreatic standard station by the number of EUS.
- 4) Detection rate of lesions in different pancreatic standard stations of endoscopic ultrasonography: It was calculated by dividing the number of patients with pancreatic lesions and Cholangiopancreatic duct lesions in the different standard stations by the number of EUS.
- 5) Missed scanning rate of adjacent vital anatomical structures in different pancreatic standard stations of endoscopic ultrasonography: It was calculated by dividing the number of important anatomy that is not scanned in the different standard stations by the number of EUS.
- 6) Mean scanning time in different pancreatic standard stations of endoscopic ultrasonography: It was calculated by dividing the total scanning time by the number of EUS.

4.3. Safety evaluation endpoints and other secondary endpoints

Adverse events shall be determined according to the definition in the code for the quality management of adverse events of medical devices. The following types of adverse events should be recorded and calculated in the hospital history and CRF. According to the CRF table, the

occurrence time, starting and ending time, intervention measures and treatment results should be filled in when recording. The severity should be referred to the previous literature and CTCAE 5.0 standard.

5. Purpose and overall design

5.1. Purpose

The purpose of this study is to develop the Endoangel with real-time pancreatic scanning navigation system in EUS. It can assist in identifying important anatomical structures adjacent to the pancreas in real time, and verify its auxiliary performance for endoscopists in clinical practice. In order to improve the quality of EUS and reduce the missed diagnosis of pancreatic lesions.

5.2. Overall design

This is a prospective, single-center, randomized controlled trial study.

6. Study process

6.1. Summary of Study Process

- If the patient meets the inclusion criteria, the patient is invited to participate in the study and then the informed consent procedure for the clinical trial is applied.
- Assess patients' eligibility based on the inclusion/exclusion criteria.
- If the patient meets the inclusion/exclusion criteria, information prior to EUS will be collected
- If the patient is enrolled, he will be randomized
- EUS is performed after informed consent. Any intraoperative adverse events are recorded on the CRF for submission and subsequent analysis.
- Follow-up will be performed from the postoperative to the study completion, as detailed in the time and event table.

6.2. Enrollment

Only after patients signed the informed consent, can the research-related procedures be conducted.

6.2.1. Informed Consent

According to the Helsinki Declaration, patients are not allowed to participate in the study without adequate informed consent. The principal investigator is responsible for ensuring that no patient was enrolled in the study without adequate informed consent. Failure to obtain informed consent and failure to document this process is considered a violation of the Helsinki Declaration and the study protocol.

All informed consent documents (ICDs) must be approved by ethics. Patient's informed consent requires documentary record on the informed consent by himself in his primary language.

The investigator or trained designated person performs a preliminary screening to determine if the patient generally meets the eligibility criteria for the study. If yes, the investigator or trained designee should recommend the patient to participate in the study. If the patient agrees to participate, they will need to sign an informed consent document.

The investigator or trained designated person should confirm that the subject understands the following points in the study:

- the purpose of research,
- potential risks or adverse events,
- Potential risks or adverse events directly related to participating the research,
- The likelihood of failure,
- Research requirements include follow-up visits,
- All rights of the subject as a participant in the clinical study.

After explaining the purpose of the study, the investigator or trained designee should answer any questions from the subject. If the subject agrees to participate, his or her wishes must be recorded by signing and dated on the EC-approved ICF, and the document should be signed and dated by the patient receiving the informed consent.

After successful completion of the informed consent process, the investigator or trained designated person will assess the eligibility of patients based on the protocol.

6.2.2. Patient Selection

All patients who underwent EUS, agreed to use EndoAngel and generally meet the study requirements were screened based on the inclusion/exclusion criteria. Patients who passed the screening were enrolled and recorded in the subject screening and enrollment tables. There is no bias in the choice of the enrolled subjects. The date of screening, the results (enrolled or not), and the primary reason for not selecting subjects (such as not meeting inclusion criteria, or not interested in participating in the study) will be recorded.

After the patients are enrolled, the research center should complete the preoperative study data collection.

It is desirable to be able to collect complete data for all enrolled patients, without those withdrawal from the study.

6.2.3 Subject identification number

Patients were numbered after signing informed consent.

The subject number begins with EA as a fixed number and is numbered starting from 0001 at the time of signing the informed consent. For example, the first patient who signed the informed consent was EA0001, and the second one was EA0002.

Once the subject identification number is assigned, the number is not reusable.

6.3 Treatment Description

This section applies to individuals who have signed an approved informed consent and have been identified as eligible to participate in this study on the basis of the inclusion and exclusion criteria. This section introduces the preoperative, surgical and postoperative management of subjects in detail.

6.3.1 Patient Screening Assessments

- 1) History
- 2) Physical examination
- 3) Hematuria pregnancy test (if required)

6.3.2 Pre-Procedure Managements

- 1) Fasting for 6 hours and water deprivation for 2 hours before examination
- 2) Routine stomach preparation.
- 3) Psychological counseling.
- 4) Performing routine anesthesia for painless gastroscopy patients.

6.3.3 Intraoperative Managements

- 1) Patient position: lateral position with appropriate restraint.
- 2) Insertion route: according to the actual situation of the subject, usually through the esophagus
- 3) Routine observation

6.3.4 Post-operative Managements

- 1) Postoperative routine nursing
- 2) Subjects were observed to wake up
- 3) Patients without pancreatic lesions and other lesions were followed up until the patient woke up and left the endoscopic room.
- 4) Patients with pancreatic lesions and other lesions detected should be followed up for 7 days after the EUS.
- 5) Record complications (if any).

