Expected effect:	ENDOANGEL's intended use is to effectively improve the quality of EUS scanning for physicians, enhance the cognitive ability of endoscopists in endoscopic ultrasound images, and reduce the missed diagnosis of lesions.
Primary Endpoint:	Missed scanning rate of adjacent important anatomical structures in pancreatic endoscopic ultrasonography
Secondary Endpoints:	
 1.Pancreatic lesions detection rate; 2.Cholangiopancreatic duct lesions detection rate 3.The average number of scanning in the pancreatic standard station of endoscopic ultrasonography 4.Detection rate of lesions in different pancreatic standard stations of endoscopic ultrasonography 5.Missed scanning rate of adjacent vital anatomical structures in different pancreatic standard stations of endoscopic ultrasonography 6.Mean scanning time in different pancreatic standard stations of endoscopic ultrasonography
Trail design:	Prospective, single-center, randomized controlled trial
Participants:	Male and female subjects aged 18 years or older will require a endoscopic ultrasonography, and voluntarily provide endoscopic ultrasonography imaging data and sign an informed consent form.
Sample size:	285 samples needed to be enrolled
Study Process:	Subjects who met all inclusion criteria and did not meet all exclusion criteria were included in the study before endoscopic ultrasonography. All included subjects signed an informed consent form. Subjects will be randomized prior to the start of the examination to either an Endoangel-assisted experimental group or a control group without Endoangel assistance. The operating physician completed the endoscopic ultrasonography according to the presence or absence of AI prompt. The recorder shall record the number of adjacent important structures, the number of standard stations, the operation time and the lesion detection etc. Follow-up will be performed for one week after the end of examination. The end time of follow-up is the end time of study. And the results are sent to an independent data analysis team for review.

[figure not shown]

Security	Safety incidents shall be evaluated and reported according to the quality management measures for clinical trials of medical devices
-----------------	--

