1.1. Time and Event Tables

Events	Screening period (d -30 [~] -1)	The day of EUS (d 0)	Follow up (d 1-14)
Informed Consent	X		
Basic characteristics	X		
Medical history/surgical history	X		
Inclusion/Exclusion Criteria	X		
Random		X	
Endoscopic Ultrasonography		X	
Concomitant treatment	X	X	
Concomitant medication	X	X	
Adverse Events		X	X
Research completed			X

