7.1. Selection of endpoints

1、The primary outcome of the study are the Missed scanning rate of adjacent important anatomical structures in pancreatic endoscopic ultrasonography.

The secondary outcomes of this study were: 1.Pancreatic lesions detection rate; 2.Cholangiopancreatic duct lesions detection rate; 3.The average number of scanning in the pancreatic standard station of endoscopic ultrasonography; 4.Detection rate of lesions in different pancreatic standard stations of endoscopic ultrasonography; 5.Missed scanning rate of adjacent vital anatomical structures in different pancreatic standard stations of endoscopic ultrasonography; 6.Mean scanning time in different pancreatic standard stations of endoscopic ultrasonography.

Adverse events in safety indicators shall be judged in accordance with relevant regulations, and serious adverse events shall be recorded and reported in accordance with regulations.

Other evaluations are detailed in the Case Report Form (CRF).

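### Section 6.3.4 stops follow-up at room exit for subjects with no lesion, while the synopsis and table 1.1 follow every subject after discharge

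*Combined protocol and SAP*

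**What the plan says.** Four places in the combined protocol and SAP define follow-up after the procedure.

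- **Synopsis, Study Process:** "Follow-up will be performed for one week after the end of examination". No subgroup is named. The synopsis adds that the end of follow-up is the end of the study.
- **Table 1.1:** the follow-up column covers days 1-14. Adverse events and completion of the research are both marked in it, with no footnote or condition.
- **Section 6.1:** "Follow-up will be performed from the postoperative to the study completion, as detailed in the time and event table".
- **Section 6.3.4, items 3 and 4:** "Patients without pancreatic lesions and other lesions were followed up until the patient woke up and left the endoscopic room", whereas "Patients with pancreatic lesions and other lesions detected should be followed up for 7 days after the EUS". Item 5 of the same list asks for complications to be recorded.

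There are also general duties to record. Section 4.3 says "The following types of adverse events should be recorded and calculated in the hospital history and CRF", and section 7.1 says "serious adverse events shall be recorded and reported in accordance with regulations". Neither sets up a contact with the subject after discharge.

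**The concern.** For a subject with no lesion, 6.3.4 cannot be followed together with the synopsis and table 1.1. No text reconciles them or states an order of precedence.

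If staff work from 6.3.4, two things follow. First, post-discharge adverse events are actively sought only in subjects with a lesion. An event at home in a lesion-negative subject reaches the CRF only if that subject happens to report it. Second, the intensity of safety ascertainment then depends on a result that arises after randomisation and that the device is meant to influence: section 7.6 anticipates more lesions found in the experimental group, and section 8.3 makes improved pancreatic lesion detection a main hypothesis. Delayed events could then be looked for in different proportions of the two arms.

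What is at stake is the completeness and comparability of descriptive safety data. The end-of-study date is also unclear for lesion-negative subjects: day 0 if 6.3.4 is combined with the synopsis definition, but days 1-14 in table 1.1. Section 6.6 records concomitant treatment up to study completion, so that period inherits the ambiguity.

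**Working it through.** **The rules side by side**

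| Source | Lesion found | No lesion found |
|---|---|---|
| Synopsis | 1 week | 1 week |
| Table 1.1 (and 6.1, which defers to it) | day 1-14 column | day 1-14 column |
| 6.3.4 items 3-4 | 7 days | ends on leaving the endoscopy room |

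For subjects with a lesion the sources can be reconciled: 7 days equals one week and fits within days 1-14. For subjects without a lesion they cannot, because 6.3.4 provides nothing from day 1 onward.

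**The plan's own figure**

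The sample size in section 8.4 reproduces. With 20% against 8%, two-sided 5%, 80% power, 1:1 allocation and unpooled variance:

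n per arm = (0.20 × 0.80 + 0.08 × 0.92) × (1.960 + 0.842)² / 0.12² = 127.3, rounded up to 128.

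The total is 256, and 256 / 0.90 = 284.4, rounded up to 285. Follow-up does not enter this calculation.

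**Size of the loss if 6.3.4 governs**

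From the documents: N = 285 and 1:1 allocation, so 142.5 per arm. The documents give neither a lesion prevalence nor an adverse-event rate. Assumptions:

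- 40% to 80% of subjects are lesion-negative (114 to 228 of 285);
- 0.5% to 2% have an adverse event that first appears after leaving the room;
- this rate does not depend on lesion status;
- there is no dropout.

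*Events not actively sought* = 285 × lesion-negative share × delayed-event rate:

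- low: 285 × 0.40 × 0.005 = 0.57
- middle: 285 × 0.60 × 0.01 = 1.71
- high: 285 × 0.80 × 0.02 = 4.56

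Widening the lesion-negative share to 10-90% gives 285 × 0.10 × 0.005 = 0.14 at the low end and 285 × 0.90 × 0.02 = 5.13 at the high end.

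*Imbalance between arms* = 142.5 × difference in any-lesion detection × delayed-event rate. For an assumed difference of 5 to 10 percentage points:

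- low: 142.5 × 0.05 × 0.005 = 0.036
- high: 142.5 × 0.10 × 0.02 = 0.285

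The direction depends on which arm detects more lesions.

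*What zero observed delayed events would exclude.* The one-sided 95% upper bound is 1 − 0.05^(1/n), where n is the number actually followed:

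| Followed after discharge | Upper bound |
|---|---|
| 57 (80% lesion-negative) | 5.1% |
| 171 (40% lesion-negative) | 1.7% |
| 256 (10% lesion-negative) | 1.2% |
| 285 (everyone) | 1.0% |

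If table 1.1 governs, everyone is followed and there is no loss.

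**The case against.** The strongest reply is that 6.3.4 was never meant as the study's follow-up schedule. It sits under 6.3, Treatment Description, which covers management around the procedure, so items 3 and 4 could be clinical aftercare. Section 6.1 points to table 1.1 as the schedule, and 6.2.1 tells every consenting subject that follow-up visits are part of the research. On that reading 6.3.4 is the outlier and one clarifying sentence would settle the matter. This has some force: 6.1 does favour table 1.1, which is why the loss is stated as conditional. But the aftercare reading is weak. Item 4 repeats the synopsis duration, item 5 puts the recording of complications in the same list, and this is the only place that gives staff post-procedure instructions by type of patient.

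A second reply is that the size rests on unsourced assumptions. That is correct. With few lesion-negative subjects the loss is about 0.1 events and the upper bound moves only from 1.0% to 1.2%. If delayed events are more frequent in subjects with a lesion, 6.3.4 already follows the higher-risk group and the estimates above are too high.

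A third reply is that little depends on it. The device is software that does not touch the patient, section 7.4 expects only the complications of routine endoscopy apart from a possible slight increase due to trial procedures, and no formal safety test is planned. Findings-based follow-up could be a defensible choice for such a device. All this limits the consequence, and the arm imbalance alone would not justify a change. It does not resolve the contradiction, since the protocol itself schedules adverse-event collection after day 0 for everyone.

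**Conclusion.** The concern holds. It is certain that the protocol contains two incompatible follow-up rules for lesion-negative subjects at a single center. The loss of safety information is conditional on staff following 6.3.4: about 0.6 to 4.6 events not actively sought under the stated assumptions, falling to about 0.1 if only 10% of subjects are lesion-negative. The arm imbalance, at 0.04 to 0.29 events in either direction, is negligible in size, although follow-up that depends on a post-randomisation outcome is poor practice in principle. The effect is confined to descriptive safety data and the end-of-study definition. The primary endpoint is measured during the EUS and is unaffected, as is N = 285. The point should be corrected, but it does not threaten the trial's main conclusion.

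**What to change.** Delete items 3 and 4 of 6.3.4. Define one adverse-event window, for example 7 days after EUS, for every randomised subject in both arms regardless of findings. Align the synopsis, table 1.1 and 6.3.4 to it, and state whether days 1-14 is the period within which the contact is made. Report adverse events by arm, descriptively, over that window.

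If the sponsor wants to keep items 3 and 4 as clinical aftercare, the text should say so and state that adverse-event follow-up runs for all subjects as in table 1.1.

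The cost is protocol wording plus one brief contact per lesion-negative subject: 114 to 228 contacts under the 40-80% assumption, which the synopsis and table 1.1 already imply. Neither the sample size nor the primary analysis changes.

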7.6. Related benefits

Subjects will be randomly assigned to an experimental group or a control group. And experimental subjects may increase the detection of pancreatic lesions and other lesions.

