8.3. Hypothetical test

The main assumptions are:

1. The use of EndoAngel can reduce the missed scanning rate of adjacent important anatomical structures in pancreatic endoscopic ultrasonography.
2. The use of EndoAngel can improve the the detection rate of Pancreatic lesions.

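### Section 6.3.4 ends follow-up at room exit for patients without lesions, in conflict with the unconditional follow-up in the synopsis and table 1.1

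*Combined protocol and SAP*

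**What the plan says.** Four places set follow-up after the EUS.

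- Section 6.3.4, items 3 and 4: "Patients without pancreatic lesions and other lesions were followed up until the patient woke up and left the endoscopic room", and "Patients with pancreatic lesions and other lesions detected should be followed up for 7 days after the EUS". Item 5 then asks for complications to be recorded, with no condition and no time limit.
- Synopsis, Study Process: "Follow-up will be performed for one week after the end of examination", followed by "The end time of follow-up is the end time of study". Neither sentence mentions lesions.
- Table 1.1: the follow-up column covers days 1 to 14. Only two rows are marked in it, adverse events and research completion, and neither mark depends on findings.
- Section 6.1: "Follow-up will be performed from the postoperative to the study completion, as detailed in the time and event table".

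No section says which rule prevails. Two other sections expect detection to rise with the device. Section 7.6 says that "experimental subjects may increase the detection of pancreatic lesions and other lesions", and section 8.3 states as a main assumption that "The use of EndoAngel can improve the the detection rate of Pancreatic lesions".

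**The concern.** A patient whose follow-up ends on leaving the endoscopy room cannot also have one week of follow-up or an adverse-event assessment between days 1 and 14. The protocol therefore gives lesion-free patients two incompatible instructions. Because the synopsis equates the end of follow-up with the end of study, the rule that staff adopt also decides when recording stops.

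At stake is the completeness of the safety data. Section 7.4 expects adverse events to be essentially those of conventional endoscopy, and every patient undergoes the EUS whatever it shows. By giving lesion patients seven days, the plan accepts that events after room exit are worth looking for. It states no reason to stop looking in the others.

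**Working it through.** **1. The rules side by side**

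| Source | Lesion found | No lesion found |
|---|---|---|
| 6.3.4, items 3-4 | 7 days | until room exit (day 0) |
| Synopsis | one week | one week |
| Table 1.1 (via 6.1) | within days 1-14 | within days 1-14 |

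In the lesion column the three rules can be reconciled, since a contact at day 7 lies inside days 1-14. In the no-lesion column they cannot. The clear conflict is with item 3.

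**2. The denominator**

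Section 8.4 gives 285 patients (20% vs 8%, two-sided alpha 5%, power 80%, 10% dropout). The unpooled two-proportion formula gives (1.960 + 0.842)² × (0.20×0.80 + 0.08×0.92) / 0.12² = 127.3, so 128 per arm and 256 in total. Then 256/0.9 = 284.4, rounded up to 285. The figure reproduces, and nothing below changes it. With 1:1 allocation there are 142.5 patients per arm.

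**3. Patients without a scheduled contact if 6.3.4 is followed**

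Let pc and pt be any-lesion detection in the control and EndoAngel arms. Their values are assumptions, because the documents give none.

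- No contact after the room = 142.5 × [(1 − pc) + (1 − pt)].
- Upper limit on missed events at an assumed 2% delayed-event risk = 0.02 × that number, out of 0.02 × 285 = 5.7 events.
- Between-arm gap in recorded events at equal true risk = 142.5 × 0.02 × (pt − pc).

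| pc / pt | No contact | Missed events (upper limit) | Between-arm gap |
|---|---|---|---|
| 30/30% | 199.5 | 3.99 | 0 |
| 50/50% | 142.5 | 2.85 | 0 |
| 70/70% | 85.5 | 1.71 | 0 |
| 90/90% | 28.5 | 0.57 | 0 |
| 30/40% | 185.25 | 3.71 | 0.285 |
| 50/60% | 128.25 | 2.57 | 0.285 |
| 70/80% | 71.25 | 1.43 | 0.285 |

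With a 10-point gain, the gap is 142.5 × 0.01 × 0.10 = 0.14 event at 1% risk and 142.5 × 0.05 × 0.10 = 0.71 event at 5% risk.

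**4. Share of delayed events not sought**

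If risk is unrelated to lesions, the share is the no-contact number divided by 285: 199.5/285 = 70% at 30/30%, falling to 28.5/285 = 10% at 90/90%. If lesion carriers have three times the risk and detection is complete and equal (p in each arm), the share is (1 − p)/(3p + 1 − p): 0.7/1.6 = 44% at 30% and 0.1/2.8 = 3.6% at 90%.

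**5. What a clean safety record would show**

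With no delayed event among n patients followed, the one-sided 95% upper limit on the rate is 1 − 0.05^(1/n).

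- n = 285: 1.05%.
- n = 85.5 (30/30%): 3.44%.
- n = 256.5 (90/90%): 1.16%.

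The last two also assume that patients with lesions represent the rest.

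**The case against.** The strongest reply is that 6.3.4 describes clinical management. Its items speak of follow-up without naming adverse events, item 5 has no lesion condition, and section 6.1 points expressly to the unconditional table. Staff who follow 6.1 lose nothing. Part of this stands: the consequences arise only if 6.3.4 is followed. But the instruction to record complications sits directly under items 3 and 4, the follow-up column of table 1.1 holds nothing clinical except adverse events, and the pointer in 6.1 does not cancel item 3.

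A second reply is that the size is assumed and may be small. Item 4 also covers lesions other than pancreatic ones, and section 3.1 enrols patients who need EUS to characterise digestive disease, so detection may be high. Sections 4.3 and 7.1 also require adverse events to be recorded, so events in patients who stay or return could still reach the CRF. This stands, and is why the range runs to 90% and the missed counts are upper limits.

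Three stronger readings are tempting, and the documents do not support them.

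- A reader might infer a biased safety comparison, since follow-up depends on a post-randomisation result expected to favour the device. At 30/40% detection the ratio of recorded events is 0.40/0.30 = 1.33, but the 2%-risk counts behind it are 1.14 vs 0.855. The gap vanishes if any-lesion detection is equal. Section 7.4 describes non-contact software with no change from routine operation, and no between-arm test of adverse events is planned.
- A reader might set the synopsis's week against days 1-14. The column can be read as a window that contains the one-week contact.
- A reader might infer that complications ending an EUS early under 6.4.2 go unrecorded. Section 6.1 requires intraoperative events on the CRF, and 4.3 requires their treatment and outcome. At most, the later window for these patients needs clarifying.

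**Conclusion.** The point holds as a conflict over safety data collection. Item 3 of 6.3.4 cannot be satisfied together with the synopsis or table 1.1, and nothing in the documents resolves it. That much is certain from the text.

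The consequence is conditional on staff following 6.3.4. Delayed complications in lesion-free patients would then not be actively sought in either arm. How many would be missed cannot be computed from the documents. Across the assumed 30% to 90% any-lesion detection, about 28 to 200 of 285 patients would have no scheduled contact. At an assumed 2% risk, at most 0.6 to 4.0 of 5.7 delayed events would be missed. Differential capture is less than one event in every case shown and zero when detection is equal. The primary endpoint is measured during the examination, so neither it nor the sample size is affected. The correction should be made, but it does not call the trial's main result into question.

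**What to change.** Replace items 3 and 4 of 6.3.4 with a single rule: every randomised patient has one adverse-event follow-up contact at one week after the EUS, within the day 1-14 window, regardless of findings. State it identically in the synopsis, table 1.1 and 6.3.4.

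The change is to wording only, with no effect on the sample size or the analysis. The added burden is one short contact for lesion-free patients (about 28 to 200 under the assumptions above), which the synopsis and table 1.1 already schedule.
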